6.2 Laboratory evaluations

6.2.1 Urine pregnancy test

In females of childbearing potential urine pregnancy tests must be confirmed negative at screening, and prior to study vaccines administration on Study Days 0, 28, and 168. A confirmatory serum pregnancy test will be required in the event of a positive urine pregnancy test. A positive serum pregnancy test will result in withdrawal of the subject from the study (per Section 4.3.1). A negative serum pregnancy test will permit the subject to continue on the study and to continue to receive the study vaccines. In women whose urine pregnancy tests is positive, no study vaccine will be administered until the confirmatory serum pregnancy tests is found to be negative.

6.2.2 Screening laboratory evaluations

The following laboratory evaluations will be done at screening:

- All potential subjects will be tested for HIV infection, HCV infection and past or current HBV infection prior to enrollment. A positive test is exclusionary, except in the case of HCV, if the subject was treated and cured (defined as documented sustained virologic response (SVR) or negative viral load ≥ 12 weeks after cessation of antiviral therapy).
- Hematology
 - White blood cell count with differential
 - o Red blood cell count
 - Hematocrit (HCT)
 - Mean cell hemoglobin (MCH)
 - Mean cell hemoglobin concentration (MCHC)
 - Mean corpuscular volume (MCV)
 - o Hemoglobin
 - o Platelet count
- Biochemistry:
 - o Blood urea nitrogen (BUN)
 - Serum creatinine
- GFR: will be automatically calculated upon input of serum creatinine value, age, gender and weight in the eCRF using the CKD-EPI Creatinine Equation (2009)²⁵
 - GFR≤ 60 mL/min/1.73 m² is exclusionary

- Alkaline phosphatase (AP), alanine transaminase (ALT: SGPT), aspartate transaminase
 (AST: SGOT), total and conjugated bilirubin, gamma-glutamyl-transferase (GGT)
- HbA1C will be tested in subjects with a known type 2 diabetes if a previous HbA1C test result is unavailable and/or is > 3 months old, in order to verify that diabetes is controlled. HbA1C >8.5 % is exclusionary.

Urinalysis:

 A urine sample will be tested for: pH, gravity, glucose, ketones, nitrites, bilirubin urobilirubin, blood, protein, red blood cell count, white cell count.

Any anomaly that would be considered of Grade 1 severity (or more) according to Appendix 4 will be interpreted within the subject's specific context (subject's medical history, physical examination, other laboratory tests) by the investigator to determine whether the subject still meets inclusion criterion # 3. Grade 3 severity or above is exclusionary, regardless of clinical assessment. One repeat testing assessment will be permitted.

6.2.3 Immunogenicity

Immunogenicity (measurement of anti-HBs, anti pre-S1 and anti pre-S2 levels and characteristics) will be assessed at baseline (V1), on Study Days 28 (V2), 56 (V3), 168(V4), 196 (V5), and on Study Day 336 (End of Study Visit – V6) in all subjects.

A validated quantitative antibody test will be utilized to measure anti-HBs levels in serum.

The assay to measure anti pre-S1 antibody and anti pre-S2 antibody is currently under development and will be validated prior to its use in the phase 3 trial.

In study subjects that have agreed for their unused blood samples to be used for future research by the study sponsor (bio banking), de-identified frozen serum aliquots will be stored in a secure biorepository held by the study sponsor for future use. De-identification is the process by which a coded sample is relabeled with a unique second code, as an added step to preserve confidentiality, with limited and restricted access to the list linking the codes. No genetic testing will be performed.

6.2.4 Sub-Studies

6.2.4.1 Clinical laboratory sub-study

At select study sites, clinical laboratory parameters (hematology, biochemistry) will be assessed one week after each vaccination with either Sci-B-Vac or Engerix-B® and compared to baseline (pre-vaccination) values, as part of a clinical laboratory sub-study. All subjects enrolled at these select sites will be required to come for three additional visits and to provide four additional blood samples, beyond those required for the main study. The clinical laboratory sub-study will include at least 10% of all subjects enrolled to the entire trial.

Blood samples for the clinical laboratory sub-study will be collected at baseline (Day 0, Visit 1) prior to receiving any study vaccine, and at each of the three additional visits (additional visits A1, A2 and A3 in Appendix 2 Schedule of Events), to be scheduled 1 week after each vaccination with Sci-B-Vac™ or Engerix-B® on Study Day 7 (-3/+7 days), Study Day 35 (-3/+7 days) and Study Day 175 (-3/+7 days), respectively. The following clinical laboratory parameters will be evaluated:

Hematology

- o White blood cell count with differential
- o Red blood cell count
- Hematocrit (HCT)

- Mean cell hemoglobin (MCH)
- Mean cell hemoglobin concentration (MCHC)
- Mean corpuscular volume (MCV)
- o Hemoglobin
- o Platelet count
- Biochemistry:
 - o Blood urea nitrogen (BUN), serum creatinine.
 - Alkaline phosphatase (AP), alanine transaminase (ALT), aspartate transaminase (AST), total and conjugated bilirubin, gamma-glutamyl-transferase (GGT)

Safety laboratory evaluations may be repeated if indicated (e.g. follow-up of a clinically significant laboratory abnormality (from baseline assessment))

6.2.4.2 Optional sub study of cell-mediated immunity directed against HBs

Cell-mediated immunity directed against HBs and related mechanistic studies will also be studied on a small subset of subjects (~50-75 subjects/treatment arm), recruited from among the subjects participating in the clinical laboratory sub-study (see 6.2.4.1 above). Participation in the sub-study of cell-mediated immunity is optional, and will require a separate consent.

Subjects who agree to participate in the sub-study of cell-mediated immunity will be asked to provide 4 additional blood samples, beyond those required for the clinical laboratory sub-study, at V1 (Study Day 0) prior to vaccination and at each of three additional visits (A1, A2, A3) 1 week after each vaccination with either Sci-B-Vac[™] or Engerix-B[®] (Study Days 7, 35, 175).

Lack of participation in the optional sub-study of cell-mediated immunity will not preclude participation the clinical laboratory sub-study or the main study.

6.2.5 Biological samples handling, analysis and storage

For the main study, the total amount of blood will not exceed 15 mL at any given visit. For select sites participating in the clinical laboratory sub-study, an additional 10 mL of blood will be required at V1 (Study Day 0) and at each of the additional study visits (A1, A2, A3) on Study Days 7, 35, and 175, respectively. For the clinical laboratory sub-study participants who also consent to participate in the optional sub-study of cell-mediated immunity, an additional 40 mL will be required at V1 (Study Day 0) and at each of the additional study visits (A1, A2, A3) on Study Days 7, 35, and 175, respectively.

Samples and accompanying documentation will not be labeled with information that directly identifies the subject but will be coded with the identification number for the subject (subject number).

Unused blood samples will be stored until the Sci-B-Vac[™] has been approved, for confirmation purposes only, for a maximum of 60 months (5 years) after the study has been completed. No genetic testing will be performed.

Study subjects will be offered the possibility to donate any unused stored blood samples for use in future research projects in HBV testing and vaccine development. De-identified bio banked frozen serum aliquots from consenting study subjects will be stored in a secure biorepository held by the study sponsor for future research. No genetic testing will be performed.

If the study subject does not agree to donate unused stored blood samples, they will not be used in other research projects and they will be destroyed once the vaccine is approved in Canada, the U.S. and Europe or after a maximum period of 5 years after the end of the study, whichever comes first.

Detailed information on biological sample handling and analysis is provided in the laboratory manual.

6.3 Study schedule of events

A schedule of events is available in Appendix 2.

6.3.1 Screening

The screening will be conducted within 28 days (4 weeks) of Visit 1. After obtaining informed consent in accordance with ICH GCPs, inclusion/exclusion criteria will be assessed and the following data/samples will be obtained:

- Medical History/ Demographics
- Physical Examination (or at Visit 1 prior to injection)
- Height and weight
- Concomitant medications
- Urine Pregnancy test (in females of childbearing potential)
- Blood sampling for screening hematology, blood chemistry and serology tests (HIV, Hepatitis C and B)
- Urinalysis

If the subject is eligible, the study staff will proceed to complete the enrollment procedures and to schedule the first vaccination visit. Study subjects will be requested not have any inactivated vaccines (e.g. influenza) 2 weeks prior to 2 weeks after each study vaccination and not to have attenuated vaccines (e.g. MMR) 4 weeks prior to 4 weeks after each study vaccination.

6.3.2 Vaccination visits

Vaccination will be done at Visit 1, 2 and 4 (Study Day 0, Study day 28 (-3 days/+7 days), and Study day 168 (+/- 7 days, respectively).

On Day 0 (Visit 1), subjects will have a blood sample collection prior to vaccine administration.

At subsequent vaccination visits (on Study Days 28 and 168), and prior to study vaccine administration, there will be a review of ongoing eligibility to receive the study vaccine and continue on the study. Diary cards will be collected (Study Day 28) and there will be a review of any local and systemic reactions. There will also be a blood sample collection prior to each vaccine administration.

Subject will remain at least 30 minutes after each vaccination to be observed for rare adverse reactions.

At each vaccination visit the following will be done:

Concomitant medications will be recorded, including other vaccines.

- A urine pregnancy test will be done in females of childbearing potential and reviewed prior to vaccination. Pregnancy test must be confirmed negative prior to study vaccine administration.
- Blood samples for Immunogenicity tests (measurement of anti-HBs, anti pre-S1 and anti pre-S2 levels and characteristics), on Study Day 0, Study Day 28 and Study Day 168 will be taken, prior to vaccination.
- Blood samples for assessment of clinical laboratory parameters will be taken on Study Day
 0, prior to vaccination (select sites).
- Vital signs will be assessed before and after the injection of study vaccine. Any abnormal vital sign after injection should be reassessed.
- Physical/History-directed physical examination will be done.
- Eligibility for receiving treatment will be reviewed by the investigator.
- Study vaccine will be administered.
- Subject will be monitored for 30 minutes after the injection.
- A diary card will be provided at each vaccination visit. In addition, at Visit 2 (Study Day 28), the diary card provided at Visit 1 will be collected and reviewed. Adverse events will be recorded in the eCRF.
- The next visit will be scheduled.
- Subjects will be reminded that they should return the diary card at the next visit and that
 they should not receive any inactivated vaccine 2 weeks prior to or 2 weeks following the
 first, second or third vaccination. Subjects will also be reminded not to have an attenuated
 vaccine between V1 (Study Day 0) and V2 (Study Day 28), or for 4 weeks after V2 or within
 4 weeks of the third vaccination on V4 (Study Day 168).

6.3.3 Safety follow-up

The study center will contact the subject by telephone 7 days (+/- 2 days) after each vaccination to assess subject's status and to remind the subject to complete the diary cards and return them at their next study visit. A scripted set of questions will be asked over the telephone to determine health status and safety clinical markers.

6.3.4 Supplemental visit(s)

Subjects may be asked to come for a supplemental visit for clinical assessment of an adverse event if warranted, as determined by the investigator. The supplemental visit will be recorded in the eCRF.

6.3.5 Immunogenicity visits

Additional immunogenicity visits will be scheduled on V3 Study Day 56 (-3/+7 days) and V5 Study Day 196 (+/-7 days). At these clinical visits, the following will also be done:

Physical/History-directed physical examination.

- Blood samples for measurement of anti-HBs, anti pre-S1 and anti pre-S2 levels and characteristics will be taken on Study Day 56 and Study Day 196.
- V3 should be scheduled at least 3 weeks after V2
- Diary card provided at the previous vaccination visit will be reviewed.
- Adverse events and the use of concomitant medications will be recorded in the eCRF.
- The next visit will be scheduled.
- At V3 (on day 56) subjects will be reminded that they should not receive inactivated vaccines
 2 weeks prior or attenuated vaccines 4 weeks prior to the next vaccination at V4 (on Study Day 168).
- V5 should be scheduled at least 3 weeks after V4

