3.3 Secondary endpoints

- SPR on Study Days, 56 and 168, 4 weeks and 20 weeks after receiving the second Sci-B-Vac[™] vaccination (just prior to receiving the third vaccination), and the SPR on Study Day 196, 4 weeks after receiving the third Engerix-B[®] vaccination
- Number (%) of subjects-reported, solicited (on the day of vaccination and during the next 6 days), unsolicited AE (on the day of vaccination and during the next 27 days), and number of Serious SAEs, medically significant events (condition prompting emergency room visit, physician visit not related to a common disease/not a routine visit or an SAE not related to a common disease) or new onset of chronic illness through Study Day 336. Adverse events will be classified by Medical Dictionary for Regulatory Activities (MedDRA) system organ class and preferred term, severity, seriousness, investigator and Sponsor causality assessment, and time since vaccination.
- Number (%) of subjects with abnormal vital signs, and/or physical examination findings compared to baseline.

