6.1.10 Recording of adverse events

- The subjects will be instructed to contact the investigator/study center staff immediately should they manifest any signs or symptoms they perceive as significant.
- During the vaccination visits (on Study Days 0, 28, and 168), the subject will be provided 28-day diary cards. On Study Day 0 they will also be provide with a measurement device template (in mm) for measuring the largest diameter of solicited local reactions (erythema [redness], swelling), and an oral thermometer for recording daily temperature (in °C or in °F) on the day of vaccination and for the next 6 days.
- Subjects will be asked to record daily the maximum pain, tenderness and pruritus [itchiness] they
 experience at the injection site on a scale from 0 to 3 (0: no pain 1: Mild discomfort to touch 2:
 Discomfort with movement 3: Significant discomfort at rest) on the day of vaccination and for the
 next 6 days.
- The subject will record body temperature (oral) and any local/systemic AEs (i.e., on the day of vaccination and during the next 6 days) or any solicited or unsolicited AEs (i.e., on the day of vaccination and during the next 27 days occurring after injection) on the 28-day diary card. The study center will contact the subject 7 days (+/-2 days) after each vaccination to assess subject status and to remind the subject to complete the diary cards and return them at the next study visit.

• The subject will be:

- Trained on how to complete the diary.
- Requested to record their individual data in their diary cards, as described above.
- Asked to provide a telephone contact, so the study center staff can contact them for the safety follow-up 7 days (+/- 2 days) after each vaccination.
- Advised that they will be asked about the occurrence of any symptoms or events requiring medical attention (i.e., requiring a doctor or emergency room visit) and the use of concomitant medication up to Study Day 336.
- Instructed to bring their diary cards to clinic visit on Study Days 28, 56, and 196 as follows:
 the diary card provided on Study Day 0 will be collected on Study Day 28; the diary card
 provided on day 28 will be collected on Study Day 56, and the diary card provided on day
 168 will be collected on Study Day 196. The staff will review the diary cards entries with the
 subject.

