6.3.7 End of study visit

The end of study visit will be performed on Study Day 336 (+/-14 days) or earlier in case of withdrawal.

- Physical/History-directed physical examination.
- Blood samples for measurement of anti-HBs, anti pre-S1, and anti pre-S2 levels and characteristics will be taken.
- SAE, AE requiring medical attention and the use of concomitant medications will be recorded in the eCRF
- In case of withdrawal: reason for withdrawal will be documented in the eCRF
- Subject will be advised that the study center staff may need to contact them in case new information, such as lack of seroprotection (anti-HBs levels <10 mIU/mL), becomes available.

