6.3.14.3 Unsolicited Adverse Events

Treatment-emergent adverse events (TEAEs) are defined as those adverse events that either start or worsen on or after the date of first vaccination.

All following TEAEs will be included in the summary tables:

• All AEs occurred on the day of vaccination (vaccination 1, vaccination 2 or vaccination 3) and during the next 27 days [date of vaccination + 27 days]

AND

^{**} Oral temperature; no recent hot or cold beverages or smoking.

^{***} When resting heart rate is between 60 - 100 beats per minute. Use clinical judgement when characterizing bradycardia among some healthy subject populations, for example, conditioned athletes.

Statistical Analysis Plan

• SAEs, medically significant events (i.e., AEs medically attended) or new onset of chronic illnesses through the date of end study

If a subject missed one or two vaccination injections, the AEs for the corresponding vaccination injections will not be included in the summary. For example, one subject missed vaccination 2, the AEs for the day of vaccination 2 and during the next 27 days will be missing and not be included in the summary tables and figures.

Solicited adverse events continuing beyond Day 7 will be coded by MedDRA and combined with the respective unsolicited adverse events.

For AEs included in the summary tables defined above, numbers of AEs will be summarized by System Organ Class (SOC) and Preferred Term, and also by severity/causality to vaccine. The summaries will be presented by vaccination (any vaccination, vaccination 1, vaccination 2 and vaccination 3) and interval of onset as follow:

- Day 1 to Day 28
 where the AEs will include AEs occurred on/after Day 1 (date of vaccination) until earliest date of (Day 28, date of next vaccination-1, end of study)
- Day 29 to end of considered interval
 where the AEs will include SAEs, medically significant events (i.e., AEs medically
 attended) or new onset of chronic illnesses occurred on/after Day 29 to earliest date of
 (date of next vaccination-1, end of study)
- Day 1 to end of considered interval where the AEs will include AEs occurred on/after Day 1 (date of vaccination) until earliest date of (date of next vaccination-1, end of study)

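### After dose 3 the 28-day diary can be collected at day 21, leaving AEs that are neither serious nor medically attended without planned collection for up to the last 7 days

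*Protocol*

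**What the plan says.** **Endpoint.** Protocol 3.3 lists "unsolicited AE (on the day of vaccination and during the next 27 days". SAP 6.3.14.3 tabulates the same window after each dose: "All AEs occurred on the day of vaccination (vaccination 1, vaccination 2 or vaccination 3) and during the next 27 days".

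**Card collection.** Under Protocol 6.1.10 the card "provided on day 28 will be collected on Study Day 56" (V3), and the card given on Day "168 will be collected on Study Day 196" (V5). Sections 6.1.10, 6.3.2 and 6.3.3 all have subjects return the card at the next visit. The telephone retrieval in 6.1.10 is for cards that have not been returned.

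**Visit timing.** Protocol 6.3.5: "Additional immunogenicity visits will be scheduled on V3 Study Day 56 (-3/+7 days) and V5 Study Day 196 (+/-7 days"). Each visit must also be at least 3 weeks after the preceding dose; for dose 3, "V5 should be scheduled at least 3 weeks after V4". Section 6.3.2 allows dose 2 on Day 28 (-3/+7) and dose 3 on Day 168 (+/-7).

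**Later contacts.** The schedule (Protocol Appendix 2, SAP 6.1) marks V4 and V5 for all AEs, but V3 and V6 only for AEs requiring medical attention. For V6, Protocol 6.3.7 says "SAE, AE requiring medical attention and the use of concomitant medications will be recorded in the eCRF".

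**Analysis interval.** SAP 6.3.14.3 runs the Day 1 to Day 28 interval "until earliest date of (Day 28, date of next vaccination-1, end of study"). The date of card return plays no part.

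**The concern.** A site can follow the plan exactly and still collect a 28-day card after three weeks. Nothing tells the subject to keep recording, to send the card in later, or to expect a closing call. For the final week of the window after dose 3, an ordinary AE that leads to no medical visit then has no planned route into the database, while the SAP treats those days like any others.

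At stake are the 28-day unsolicited AE frequencies, which the SAP presents separately by vaccination. They would be somewhat too low, and coverage would differ between doses and with how early sites book V3 and V5.

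**Working it through.** **Convention.** Post-dose day 0 is the vaccination day and the window is days 0-27. Shortfall = max(0, 28 - gap), where gap = collection-visit day - dose day. The visit day counts as not fully covered, so a 21-day gap covers days 0-20 in full and leaves the rest of day 21 plus six whole days (22-27).

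**The plan's own figure.** 1 + 27 = 28 days. The nominal gaps agree: 56 - 28 = 28 and 196 - 168 = 28. The plan is consistent at nominal dates; the problem comes from the windows.

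**Permitted days** (Protocol 6.3.2, 6.3.5): V2 25-35; V3 53-63; V4 161-175; V5 189-203; V6 322-350 (Day 336 +/-14).

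**Dose 3 (V4 to V5)**
- Shortest gap: 189 - 168 = 21 days, reachable for any V4 on Days 168-175. Shortfall 28 - 21 = 7 days, or 7/28 = 25% of the window.
- All pairs: 15 x 15 = 225. The 3-week rule removes 28, leaving 197. Pairs with a gap of 21-27 days: 8+9+10+11+12+13+14 = 77, and 77/197 = 39%.
- Mean shortfall over the 197 pairs: (14+26+36+44+50+54+56)/197 = 280/197 = 1.42 days.
- With V4 fixed on Day 168 and V5 even over Days 189-203: (7+6+5+4+3+2+1)/15 = 1.87 days.
- Next contact after a 21-day gap (V5 on Days 189-196): 322 - 196 = 126 days (18 weeks) to 350 - 189 = 161 days (23 weeks).

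**Dose 2 (V2 to V3)**
- A 21-day gap needs V2 on Days 32-35 with V3 on Days 53-56. With V2 on Day 28 the shortest gap is 53 - 28 = 25 days, a shortfall of 3.
- All pairs: 11 x 11 = 121, less 6 under the 3-week rule = 115. Pairs with a gap under 28 days: 4+5+6+7+8+9+10 = 49, and 49/115 = 43%.
- Mean shortfall: (10+18+24+28+30+30+28)/115 = 168/115 = 1.46 days.
- Next contact after a 21-day gap is V4, 161 - 56 = 105 days (15 weeks) to 175 - 53 = 122 days later. It asks for all AEs, but from memory and without a card.

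**Dose 1 (V1 to V2)**
- Earliest V2 is Day 25, a shortfall of at most 3 days. If dose 2 is given that day, a new card starts and the SAP closes the dose-1 interval the day before. Those days therefore go uncollected only if dose 2 is not given.

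**What the SAP would show.** The completeness analysis in SAP 6.3.14.1 concerns solicited events to Day 7. Its count of subjects providing cards makes no distinction for a card handed in at day 21, so short coverage for unsolicited AEs would not be visible in any planned table.

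**The case against.** A reader might infer that the last week of the endpoint is simply unobserved and never recovered. The documents do not support that. Protocol 7.2.4 has SAEs, medically significant events and new onset of chronic illness documented to the last visit. V6 asks about medically attended AEs. Section 7.2.1 has any AE volunteered at any visit entered in the eCRF, and 6.1.10 tells subjects to contact the site about symptoms they regard as significant. All of this stands, and it confines the gap to AEs that are neither serious nor medically attended and are not volunteered.

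A reader might also put the typical dose-2 loss at several days. With every V2 at its latest day (35), V3 falls 21-28 days after the dose and the mean shortfall is 28/8 = 3.5 days. That is an extreme case: with V2 on Day 28 and V3 even over Days 53-63 it is (3+2+1)/11 = 0.55 days.

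Finally, safety is descriptive with no hypotheses (Protocol 9.8), the windows are identical in both blinded arms, and randomization is blocked within site (9.2). Early-booking sites should therefore affect both arms alike. This also stands: it rules out a claim of demonstrated bias in the vaccine comparison. It does not reconcile a 28-day endpoint with collection permitted at 21 days.

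**Conclusion.** The gap is real and narrow. After dose 3, AEs that are neither serious nor medically attended can lack planned collection for up to 7 of 28 days, with no unusual dose timing needed. After dose 2 the same maximum requires a late V2, and V4 still offers late all-AE collection. After dose 1 the card can be at most 3 days short.

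The 39% and 43% describe permitted date pairs, not predicted proportions of subjects. The 1.4 to 1.5 days (about 5% of 28) assume all pairs equally likely; actual visit dates are unknown. These are days of coverage, and the documents give no AE rate from which to convert them to missed events. The expected effect is a modest undercount with uneven coverage between doses, similar in both arms.

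**What to change.** **Protocol 6.1.10 and 6.3.5.** Keep the visit windows. When V2, V3 or V5 falls before 28 days after the dose, review the card at the visit, have the subject keep recording to day 27, and complete it by one telephone contact, extending the retrieval already in 6.1.10. At V2 this matters only if dose 2 is not given that day.

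**SAP 6.3.14.3.** Report, by dose and arm, the number of subjects with full 28-day diary coverage.

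**Schedule of events.** Reconcile footnote (f) at V3, which limits collection to AEs requiring medical attention, with the dose-2 diary review and AE recording that 6.3.5 places at that visit.

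Two apparently simpler changes should be avoided. A 28-day minimum for V5 would move the primary-endpoint blood draw: with V4 on Day 175, only Day 203 would remain. Ending the SAP's Day 1 to Day 28 interval at card return would remove real events, such as an SAE on post-dose day 25 after a day-21 V5, and so deepen the undercount.

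**Cost.** One short call for early attenders and one extra SAP table line.
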